### 5.2 Derived Variables

Appropriate derived variables will be created as needed for study data summary and reporting. These are discussed in the section describing the analysis of the variable.

### 5.3 Missing Values

Every effort will be made to obtain complete follow-up data for every subject; however, as these are point-in-time surveys completed by the subject, it will not be possible to retrieve responses to missed survey items. No imputation of missed items or surveys is planned for the primary analysis; however, sensitivity analysis involving imputation of missed values may be undertaken if warranted.

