#### 4.0 STUDY WITHDRAWAL

Subjects may be terminated or withdrawn from the study for the following reasons:

- Voluntary withdrawal – meaning that the subject voluntarily chooses not to further participate in the study
- Lost to follow-up – meaning that the subject is more than one month late (beyond the late data collection window) and 3 documented attempts to contact the subject are unsuccessful. A subject who misses a follow-up time point but completes the questionnaires for a subsequent time point will no longer be considered lost to follow-up.
- In the physician's opinion, it is not in the best interest of the subject to continue study participation.
- Subject death.

Any study subject who does not complete the questionnaires for a specific data collection follow-up should be contacted by site personnel to determine the reason for the missed follow-up. The reason for the missed follow-up should be determined and documented in the subject's study records. All subjects enrolled (including those withdrawn or lost to follow-up) shall be accounted for with appropriate documentation.

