### 5.1 Analysis Populations

All eligible subjects who provided informed consent and completed at least 1 survey will be included in the analysis population. A second nonenrolled population will be defined as those subjects enrolled in the TP258 study that chose not to enroll in this extended follow-up study. The purpose of the nonenrolled population is to allow comparison of characteristics of subjects who self-selected to enroll in the follow-up study with those who chose not to enroll in the follow-up study.

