### 5.7 Primary Analysis

Mean NOSE scores at baseline and each follow-up evaluation will be calculated to show the time course progression of improvement. Repeated measures analysis of variance (ANOVA) will be used to test for differences from baseline to follow-up evaluations. The statistical significance level will be set at 5% (p-value < 0.05).

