### 5.8 Secondary Analyses

Appropriate statistical techniques such as Student's t-test and ANOVA will be used for continuous outcome measures. Categorical and binomial outcomes will be examined using Fisher's exact test,  $\chi^2$ , or binomial tests. All analyses of secondary outcomes measures are exploratory for informational purposes only. No adjustments for multiple comparisons will be applied.

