#### Nasal Obstruction Symptom Evaluation (NOSE)

The number and proportion (percent) of treatment responders ( $\geq 15$ -point improvement (decrease) in NOSE score from baseline to each follow-up visit) will be calculated.

Mean percent improvement from baseline to each follow-up evaluation will be calculated.

NOSE scores will also be summarized as number of subjects and percentage falling in each category (mild, moderate, severe, extreme) at baseline and each follow-up evaluation.

Responses to individual questions of the NOSE will be summarized as number of subjects and percentage falling in each response category (Not a Problem, Very Mild Problem, Moderate problem, Fairly Bad Problem, Severe problem) at baseline and each follow-up evaluation.

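### SAP 5.7 reports plain visit means and a repeated measures ANOVA of unstated form, so the size of the 24-month NOSE benefit can depend on who answered

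*SAP*

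**What the plan says.** SAP 5.7 sets out the primary analysis in two steps. First, "Mean NOSE scores at baseline and each follow-up evaluation will be calculated to show the time course progression of improvement". Second, "Repeated measures analysis of variance (ANOVA) will be used to test for differences from baseline to follow-up evaluations". It gives no covariance structure, no rule for subjects with incomplete visits, no 24-month contrast and no confidence interval.

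Three other provisions decide who enters those means:

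- SAP 5.1: "All eligible subjects who provided informed consent and completed at least 1 survey will be included in the analysis population".
- Protocol 4.0: "A subject who misses a follow-up time point but completes the questionnaires for a subsequent time point" is no longer treated as lost to follow-up, so different subjects can contribute to different visits.
- SAP 5.3: "No imputation of missed items or surveys is planned for the primary analysis; however, sensitivity analysis involving imputation of missed values may be undertaken". The sentence ends by making that sensitivity analysis conditional on being warranted. It names no trigger and no method.

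SAP 5.8 counts responders by a 15-point "improvement (decrease) in NOSE score from baseline to each follow-up visit" but does not state the denominator.

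The plan does contain safeguards. SAP 5.3 promises that "Every effort will be made to obtain complete follow-up data for every subject", Protocol 4.0 has sites contact anyone who misses a follow-up, and SAP 5.6 compares enrolled with nonenrolled subjects.

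**The concern.** Durability is the only objective (Protocol 2.3, SAP 2), and SAP 3.1 confirms that there is no control group. The NOSE level at the later visits and its change from baseline are therefore the result.

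A plain 24-month mean is a mean over those who replied at 24 months. If subjects whose obstruction has returned are less likely to reply, the mean looks better than the cohort really is. None of the safeguards corrects for this. Retention effort and contact after a missed survey may reduce the loss but do not adjust for what remains. The SAP 5.6 comparison concerns who joined the follow-up study, not who stayed to 24 months.

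The change from baseline has a further problem, because methods that all go by the name repeated measures ANOVA treat incomplete subjects differently. What is at stake is the stated size of the durable benefit and its precision.

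**Working it through.** **The plan's own figure.** The only sample figure is the maximum of 49 (50 parent-trial patients less one: Protocol 2.4, SAP 3.2). It is a head count with no power calculation behind it. No mean, SD, correlation or dropout rate is given, so every input below except 49 and the 15-point step is an assumption.

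**Step 1: identity, no distribution assumed.** Bias of the observed 24-month benefit = f × d, where f is the share of subjects missing and d is the difference in mean benefit between those observed and those missing. With d = 15 points:

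- 5 of 49 missing: 0.102 × 15 = 1.5 points.
- 10 of 49 missing: 0.204 × 15 = 3.1 points.

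The bias is zero if nobody is missing or d = 0.

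**Step 2: bias by method.** Assumed inputs:

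- Means 75 falling to 35, and 70 falling to 40; scores rounded to steps of 5 and held within 0 to 100 (true change about -39 and -30).
- Everyone has a 12-month score; nested dropout before 18 and 24 months with equal hazards, 20% in total.
- Logistic slope 1 per SD of worse NOSE (odds ratio e^1 = 2.7).
- SD baseline/follow-up, then correlation baseline to follow-up/between follow-ups: A 15/20, 0.4/0.6; B 15/22, 0.2/0.7; C 15/22, 0.2/0.8.
- 300,000 simulated subjects per run.

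The entries are points at 24 months; positive means too favourable.

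| Dropout follows | Setting | Plain mean | Change, incomplete subjects dropped | Change, univariate subject + visit | Change, likelihood mixed model |
|---|---|---|---|---|---|
| Last observed score | A | 2.2 | 1.1 | -0.2 | 0.0 |
| | B | 2.8 | 2.2 to 2.3 | 0.4 | 0.0 |
| | C | 3.2 | 2.7 | 0.8 | 0.0 |
| Unseen score | A | 3.0 | 1.9 | 1.3 | 1.5 |
| | B | 3.5 | 2.9 | 1.6 | 1.5 |
| | C | 3.6 | 3.1 | 1.6 | 1.1 |

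With weaker selection (slope 0.5, odds ratio 1.65) on the last observed score, settings A and B give 1.2 to 1.5 for the plain mean and 0.6 to 1.3 with incomplete subjects dropped. With 10% dropout at slope 1 the plain mean is off by 1.1 to 1.5, and with 30% by 3.3 to 4.2 (A and B).

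A separate run at n = 49 used other assumed inputs (baseline 75, SD 12; follow-up 30, SD 20; correlation 0.5 or 0.7 between follow-ups). At about 22% missing it gave the same pattern: plain means 2.3 to 2.9, incomplete subjects dropped 1.5 to 2.2, mixed model 0.0 to 0.2.

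**Step 3: standard error of the univariate form.** It uses a pooled variance for a difference, 2 × (mean variance - mean covariance) over the four time points. The true variance of the baseline to 24-month difference is var(baseline) + var(24 months) - 2 × covariance.

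- A: 2 × (356.25 - 180) = 352.5 against 225 + 400 - 240 = 385. Ratio of standard errors √(352.5/385) = 0.957.
- B: 2 × (419.25 - 202.4) = 433.7 against 225 + 484 - 132 = 577. Ratio 0.867.
- C: 2 × (419.25 - 226.6) = 385.3 against 577. Ratio 0.817.

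The pooled standard error is thus about 4%, 13% and 18% too small. With all 49 complete, the 95% half-widths are 5.3 against 5.6, 5.9 against 6.9, and 5.6 against 6.9 points.

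**Step 4: what the mixed model leaves.** If dropout follows the unseen score, about 1.1 to 1.5 points remain. With 20% missing, shifting the imputed scores worse by s moves the mean by 0.2 × s. The offsetting shift is therefore 1.05/0.2 = 5.3 to 1.53/0.2 = 7.6 points. A 15-point shift moves the mean by 3.0, so shifts of 5, 10 and 15 bracket the residual under these inputs.

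**Step 5: responder denominator.** In the Step 2 runs with dropout on the last observed score, the observed rate is 1.0 to 4.0 percentage points too high across A to C. As an outer bound, counting missing as non-response lowers an observed rate by rate × missing/49:

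- 5 missing: 0.8 × 5/49 = 8.2 to 0.9 × 5/49 = 9.2 percentage points.
- 10 missing: 0.8 × 10/49 = 16.3 to 0.9 × 10/49 = 18.4 percentage points.

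These are bounds, not estimates of bias.

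**The case against.** The strongest reply is that SAP 5.7 does name its method, and that SAP 5.1 points towards a form that keeps incomplete subjects. A reader might infer that the plan prescribes a complete-case analysis. It does not: an ANOVA that discards anyone with a missed survey would fail to analyse the population that SAP 5.1 defines. Among forms that keep those subjects, the bias in the change is small when dropout follows observed scores (0.8 too favourable to 0.2 too unfavourable, or zero). SAP 5.7 does not exclude a mixed model, so for the change the remedy may be clarification only. That stands. It does not rescue the plain visit means.

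The mixed model is also no cure-all. When dropout follows the unseen score, it is slightly worse on bias than the univariate form in setting A (1.5 against 1.3). Its clearer gain is a correct standard error, and SAP 5.7 plans no interval. That stands too, and is why a sensitivity analysis is needed beside it.

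The simulation simplifies. It gives everyone a 12-month score and nested dropout, which the plan does not require, and it omits the 26-week score from TP258. Adding that score brings the univariate bias to between 0.6 too favourable and 0.1 too unfavourable for dropout on the observed score, and to 1.1 to 1.3 too favourable on the unseen score. The likelihood model then gives 0.0 and 0.9 to 1.3. The pattern holds with somewhat smaller numbers.

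Finally, the effects are modest: mostly under one 5-point step of the scale and well under the 15-point responder threshold. The responder rate is a secondary outcome, and SAP 5.8 says "All analyses of secondary outcomes measures are exploratory for informational purposes only". Both points limit the weight of the concern.

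**Conclusion.** The concern holds in a limited form, and acting on it is a cheap improvement. Followed as written, the plan reports a 24-month mean that describes only those who replied. It also leaves open which ANOVA supplies the change and whether any sensitivity analysis is done.

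Under the assumed 20% dropout tied to the last observed score, the plain mean is about 2 to 3 points too favourable. The bias in the change is about 1 to 3 points if incomplete subjects are dropped and close to zero otherwise, though the univariate form may understate its standard error by 4 to 18%. If loss is unrelated to outcome, there is no bias.

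Two stronger readings are not supported. A reader might infer that the finding of improvement itself is at risk. With an assumed observed benefit of 45 points and 20 of 49 missing with no benefit at all, the benefit over all 49 would still be 45 × 29/49 = 26.6 points, so significance against baseline would probably not change. A reader might also infer from the past tense in SAP 1 that the model will be picked after the scores are seen. The documents do not say when the choices were made; they only leave room for the doubt.

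**What to change.** (a) In SAP 5.7, make the primary estimate the model-based mean and change at each visit, with 95% intervals and the number answering. Use a likelihood-based mixed model on baseline and all observed follow-up scores: visit as a factor, unstructured covariance, Kenward-Roger degrees of freedom, and compound symmetry with a robust standard error as fallback if it does not converge. State whether the TP258 26-week score enters the model and how a NOSE form with missed items is treated. Show the plain means beside it, labelled observed cases.

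(b) In SAP 5.3, replace the optional sensitivity analysis with one fixed analysis: multiple imputation of missing NOSE totals from baseline and observed visits, with imputed values shifted worse by 5, 10 and 15 points. State that the mixed model removes only part of the bias if loss follows the unseen score.

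(c) In SAP 5.8, show the observed-case responder rate with its n beside the rate over the whole analysis population with missing counted as non-response. Label the second a conservative bound on an exploratory outcome.

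State whether these choices were made before the scores were seen.

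Cost: SAP wording and standard code in SAS 9.4, already named in SAP 5.5, and no new data. The downside is a little more analysis work, possibly slightly less favourable figures, and somewhat wider intervals than a pooled ANOVA (mean full width about 13.6 against 12.3 points in setting B at n = 49 with dropout on the last observed score).

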### 5.4 Data Collection and Quality Assurance

Completed NOSE and Quality of Life surveys on case report forms will be monitored for correct score calculation by qualified Aerin Medical personnel and qualified contract personnel. Data from the Case Report Forms will be entered and stored in an electronic database (Excel).

### 5.5 Statistical Software

SAS 9.4 (SAS Institute, Cary, NC) will be used to create datasets from the excel database for reporting and analysis. Analyses will be performed using SAS 9.4 (SAS Institute, Cary, NC) and SigmaPlot 14.0 (Systat Software, Inc., San Jose, CA).

### 5.6 Demographics and Baseline Characteristics

Demographic and baseline data are available from the TP258 study and will be summarized separately for the enrolled analysis population and the nonenrolled population and examined for potential differences between enrollees and nonenrollees. Discrete variables will be described as frequencies and percentages at each level of the categorical variable. Continuous variables will be summarized descriptively (n, mean, median, standard deviation, minimum, and maximum).

### 5.7 Primary Analysis

Mean NOSE scores at baseline and each follow-up evaluation will be calculated to show the time course progression of improvement. Repeated measures analysis of variance (ANOVA) will be used to test for differences from baseline to follow-up evaluations. The statistical significance level will be set at 5% (p-value < 0.05).

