### 2.7 Types of Assessments

After patients have had the opportunity to ask questions and receive answers, and the study informed consent form is signed, the following evaluations will be completed:

- The Study Staff will administer or ask that patients complete the Nasal Obstruction Symptom Evaluation (NOSE) scale and a brief Aerin Medical Quality of Life questionnaire. These tools can be administered either in the office, by mail or via a phone call.
- These tools will be administered at 12, 18 and 24 months ( $\pm$  6 weeks) after study treatment with the Vivaer Stylus

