## 3 STUDY DESIGN

### 3.1 Overview

This investigation was a prospective extended follow-up study of subjects who had participated in the TP258 multicenter trial to evaluate the safety and efficacy of the Vivaer Stylus. Subjects were followed to the 26-week endpoint in that study. Subjects agreeing to participate in this follow-up study were to provide self-evaluation NOSE and quality of life measures at 12, 18, and 24 months after the treatment procedure. There was no concurrent control population or blinding in either the original TP258 study or in this extended follow-up study.

Self-administered evaluations were scheduled for 12, 18, and 24 months after the treatment procedure. Evaluations could occur in person with study personnel, by phone, or by mail.

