**Compared to before you had the procedure, how often do you suffer from the following conditions?**

		Very Rarely/ Never	Rarely	Occasionally	Frequently	Very Frequently
1.	Headaches					
2.	Sinus infections					
3.	Sore throat					
4.	Post nasal drip					

**Compared to the time prior to when you had the procedure, how often have you used each of the following products to help you with nasal congestion/difficulty breathing through your nose?**

		Much less frequently	Less frequently	About the same	More Frequently	Much More Frequently
1.	Oral medications (antihistamines, oral decongestants)					
2.	Nasal sprays (nasal steroids, inhaled decongestants)					
3.	Nasal breathing strips (for example, BreatheRight® Strips)					

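### Week 26 and month 18 fall about half a year from each subject's procedure date, so comparisons that use them may mix season with benefit if procedures were bunched and NOSE is seasonal

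*SAP*

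**What the plan says.** On timing, SAP 3.1 says of the parent study TP258: "Subjects were followed to the 26-week endpoint in that study". For this study it says: "Self-administered evaluations were scheduled for 12, 18, and 24 months after the treatment procedure". Protocol 2.7 agrees ("These tools will be administered at 12, 18 and 24 months") and allows 6 weeks either side, counted from the Vivaer treatment.

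On analysis, SAP 5.7 describes the visit means as follows: "Mean NOSE scores at baseline and each follow-up evaluation will be calculated to show the time course progression of improvement". The test is then given: "Repeated measures analysis of variance (ANOVA) will be used to test for differences from baseline to follow-up evaluations". The section has no covariate for calendar date or season and names no contrast between one follow-up visit and another. The one optional check on a nuisance factor is for site (SAP 5.9).

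SAP 3.1 states that neither study had a control group, and the opening of SAP 5 makes the comparison a within-subject one, before against after. The objective in SAP 2 is whether benefit lasts, and SAP 1 frames this as persistence past the six months already studied.

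**The concern.** For a given subject, baseline (taken as close to the procedure), month 12 and month 24 share a time of year, and week 26 and month 18 share the opposite one. Nasal symptoms can have an allergic or infective part that varies over the year. In an uncontrolled before-after design, nothing removes such a cycle unless it averages out because subjects were treated throughout the year.

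If it does not average out, two readings are exposed:

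- Month 18 against baseline, which SAP 5.7 tests, could come out too large or too small. The month-18 responder count and percent improvement in SAP 5.8 share this exposure.
- Week 26 against month 12 or 24, which is the natural way to ask whether benefit held after TP258, crosses seasons. A real fade could be hidden, or an apparent fade created.

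**Working it through.** The documents give no seasonal figure, standard deviation or power calculation, so there is no figure of the plan's own to reproduce. The figure of 49 (SAP 3.2) is the number who completed TP258, not a calculated sample size.

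**Step 1: position in the year.** Phase = days / 365.25 × 360°, counted from the procedure.

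- Week 26: 182 / 365.25 × 360 = 179°.
- Month 18: 180°.
- Months 12 and 24: 0°.
- The 6-week window is 42 / 365.25 × 360 = 41° either side. Month 18 therefore stays within 139° to 221°, and months 12 and 24 within 41° of the procedure date.

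The half-year offset is simple calendar arithmetic and survives the window.

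**Step 2: effect on the mean, under assumptions.** Assume an annual cycle A·cos(phase) in NOSE, where A is half the peak-to-trough swing, and procedure dates spread evenly over w months. The seasonal part of the mean is then multiplied by R = sin(πw/12) / (πw/12). It reverses sign half a year later, so the largest bias in a half-year contrast is 2·A·R.

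SAP 4.1 multiplies the summed item scores by 5, so one item moving one level is 5 points. A 5-point swing is A = 2.5, and a 10-point swing is A = 5.

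| Procedures spread over | R | 5-point swing: 2 × 2.5 × R | 10-point swing: 2 × 5 × R |
|---|---|---|---|
| 3 months | 0.900 | 4.5 | 9.0 |
| 6 months | 0.637 | 3.2 | 6.4 |
| 9 months | 0.300 | 1.5 | 3.0 |
| 12 months | 0 | 0 | 0 |

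For scale, the responder threshold in SAP 4.1 is 15 points.

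These are maxima, reached only if the procedures centred on the seasonal peak or trough. Averaged over an unknown phase (factor 2/π), the entries for 3, 6 and 9 months become about 2.9, 2.0 and 1.0 for the 5-point swing, and 5.7, 4.1 and 1.9 for the 10-point swing.

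**Step 3: effect of the visit window.** With visits spread evenly over the 6 weeks either side, the visit's seasonal part is multiplied by J = sin(0.7225) / 0.7225 = 0.915, where 0.7225 = 2π × 42 / 365.25.

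- Month 18 versus baseline: at most A·R·(1 + J). For w = 3 this is 2.5 × 0.900 × 1.915 = 4.31, or 8.62 for A = 5. For w = 6 it is 3.05 or 6.10.
- Months 12 and 24 versus baseline: at most A·R·(1 − J). For w = 3 this is 5 × 0.900 × 0.085 = 0.38 for A = 5, and 0.19 for A = 2.5.
- Extreme case for months 12 and 24: if every visit sat at one edge of the window and procedures fell on one date, the bias could reach 2·sin(0.7225/2)·A = 0.707·A, which is 1.8 points for A = 2.5 and 3.5 for A = 5.

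**The case against.** The strongest reply is that both drivers of the bias are assumed. Neither document gives a procedure date. The offset is from each subject's own procedure, not from a shared calendar season, so with procedures spread over the year the artefact in the mean vanishes and season only adds within-subject variation. Nor does either document say that NOSE is seasonal in these subjects, and SAP 3.2 attributes their symptoms to the internal nasal valve. All of this stands, and it makes the point conditional.

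A reader might take the survey items on antihistamines, decongestants and nasal steroids (SAP Figure 1) as proof that the sponsor expected seasonal disease. They do not show that. The question is about products used for congestion or difficult breathing, and it also lists breathing strips, a mechanical aid. The items make a seasonal part plausible in some subjects and no more.

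It can also be said that little of the planned inference is exposed. Of this study's three visits, only month 18 is out of season with baseline. SAP 5.7 does not name week 26, and its inclusion is a reading of what counts as a follow-up evaluation. That is right, and the month-18 point does not depend on it. But the objective asks whether benefit persists, and readers will compare later visits with the end of TP258 whether or not a test is planned.

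Finally, season is only one of several time-varying influences in a study that openly has no control. That is true, but this one has a known period and can be largely removed by choosing which visits to compare.

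**Conclusion.** The point holds as a conditional one and is a modest improvement to the plan. The half-year offset is certain. Whether it biases any mean depends on bunched procedure dates and on a seasonal cycle in NOSE, and the documents give neither. Over the assumed swings of 5 to 10 points, the largest bias in the mean for month 18 versus baseline, or for week 26 versus month 12 or 24, runs from 1.5 to 9.0 points for procedures spread over 9 down to 3 months. It is about zero for a full year's spread.

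Two stronger readings should be avoided. One is that the planned time course is in fact distorted by season; the documents do not show that either condition is met. The other is that the long-term result is undermined. Months 12 and 24 versus baseline are approximately season-matched and largely unaffected. That is not the same as wholly unaffected: it requires that baseline was close to the procedure date, an interval that is not stated, and that visits did not all fall at one edge of the window.

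**What to change.** In SAP 5.7, add two paired contrasts with 95% CIs: month 18 minus week 26, using the TP258 score, and month 24 minus month 12. Make these the main support for any statement that benefit persisted or faded between follow-up visits. Each pair is about a year apart and so approximately season-matched. The first covers the period after the six months already studied, which month 24 minus month 12 alone would miss. They are useful even if season has no effect, because SAP 5.7 at present tests only against baseline.

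Tabulate TP258 procedures by calendar month. If they are bunched, state in the report that month 18 versus baseline, and week 26 versus month 12 or 24, cross seasons. A model with seasonal terms is not worth requiring: it would be usable mainly when procedures span most of the year, and the bias is then already small.

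The cost is SAP wording, two contrasts and one table. No new visits are needed, and visit dates are already required to apply the 6-week window. The drawback is limited precision with at most 49 subjects. For an assumed standard deviation of the paired difference of 15 to 25 points, the 95% CI half-width with all 49 is 2.01 × 15 / √49 = 4.3 to 2.01 × 25 / √49 = 7.2 points, and wider with fewer subjects.
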